**Feasibility and initial efficacy of a wheelchair exercise-training intervention for
persons with multiple sclerosis**

NCT05888727

Version Date: 06/17/2024

Protocol Title: Feasibility and initial efficacy of a wheelchair exercise-training intervention for persons with multiple sclerosis

Principal Investigator: [name]

Co-Investigators: [name] & [name]

Study Coordinator: [name]

Population: Twenty-four adults with multiple sclerosis who use wheelchairs for mobility in Texas

Number of Sites: UTHealth Houston

Study Duration: 2 years

Subject Duration: 6 months

General Information

- The proposed study will examine the feasibility of a stakeholder-informed, home-based, remotely supported and supervised exercise training program for wheelchair users with multiple sclerosis (MS). The proposed exercise training program was developed in partnership with community members using semi-structured interviews, a community advisory board, and focus group feedback wherein community members provided insights to develop and refine an exercise training program that suit the needs and preferences of wheelchair users with MS.

Background Information

- [name] recently initiated a targeted agenda for creating an exercise training intervention that could be assist in managing MS consequences and optimizing health and well-being among wheelchair users with MS (1-3). [name] first conducted a qualitative study that explored the needs and preferences for exercise training among 20 wheelchair users with MS (1). Participants expressed interest in a home-based, remotely supported and supervised exercise program that included strength and aerobic training. This provided a foundation for [name] NIH F32 fellowship, guided by [name] and [name], that created the first wheelchair exercise training program for persons with MS. The F32 research included two phases of community-engaged feedback to refine and finalize the stakeholder-informed exercise training program. In Phase I, we convened a Community Advisory Board (CAB) of 10 persons with MS who completed 5 weekly meetings and provided feedback on the primary components of the program: exercise prescription, equipment, and behavioral coaching (2). [name] updated the intervention materials based on feedback received during CAB meetings and in Phase II we convened three focus groups to refine and verify the stakeholder perceptions regarding the appropriateness of the exercise program

(3). The collective process yielded a novel wheelchair exercise training program that is ready to be examined for feasibility before testing within a formal clinical trial.

- Ultimately, this study extends [name] line of research and may initiate a significant paradigm shift in rehabilitation research and practice by providing a critically needed home-based exercise training program for enhancing health, quality of life, participation, and independence of wheelchair user with MS.

Objectives

- To examine the feasibility, acceptability, and initial efficacy of a stakeholder-informed, home-based, remotely supported and supervised exercise training program for wheelchair users with multiple sclerosis (MS) compared to an attention/contact wellness control program.
- Feasibility will be operationalized using ongoing assessment of recruitment, retention, and safety. We hypothesize that the intervention will be feasible in terms of reaching recruitment goals (n=24; 12 per group) within a one-year period, retaining ≥80% of those participants through the full 16-week study period, and safe in terms of <10% of participants reporting adverse events. We are defining our recruitment goals as participants who matriculate and are randomized, therefore we aim to consent up to 28 participants.
- Acceptability will be operationalized as participant satisfaction and perceptions measured in post-intervention formative surveys and interviews. We hypothesize that a greater proportion of participants in the SPIN exercise training condition will report high satisfaction and positive perceptions regarding the exercise training program compared with the attention/contact wellness control condition.
- The study will further examine changes in scientific outcomes of interest (i.e., metabolic health, MS symptoms, and exercise behavior change) for determining effect size and sample size estimates in powering a larger clinical trial. We hypothesize that the SPIN exercise training intervention program will lead to greater improvements in metabolic health outcomes (i.e., HbA1c, cholesterol, glucose, and triglycerides), MS symptoms (i.e., fatigue, pain, depression, and quality of life) and exercise behavior compared to the attention/control wellness program.

Study Design

- Parallel group, randomized controlled trial

- The study is funded for a 2 year period and participants will be involved in study procedures for approximately 6 months.
- The primary outcome of interest is feasibility (i.e., recruitment, retention, and safety). The secondary outcome of interest is acceptability (i.e., participant satisfaction and perceptions).
- The tertiary outcomes of interest are scientific outcomes of initial efficacy(i.e., metabolic health, MS symptoms, and exercise behavior).
- Safety will be assessed in terms of incidence of participants reporting adverse events.

Study Population

- Eligibility criteria: (a) diagnosis of MS; (b) self-reported use of a wheelchair (i.e., manual wheelchair, power wheelchair, or scooter) ≥50% of the time; (c) age of 18 years or older; (d) relapse free for the past 30 days; and (e) being non-active defined as not engaging in regular physical activity (30 minutes accumulated per day) on more than 2 days of the week during the previous 6 months (i.e., not meeting current physical activity guidelines for MS). During telephone screening participants will complete an exercise pre-participation health screen and if participants report any symptoms or conditions contradictory of exercise then physician clearance will be required before enrollment.
- Inclusion/exclusion criteria align with the samples that were engaged in our community-engaged foundational studies and numerous clinical trials in persons with MS and other wheelchair users such as spinal cord injury.
- Participants will be recruited using clinic visits at UTHealth Houston and Harris Health MS clinics and flyers in the local community. Specifically, [name] will facilitate contact with potential participants in the UTHealth Houston and Harris Health clinics.

Study Procedures

- Interested participants will contact the Study Coordinator for a telephone screening, which includes a comprehensive description of the study followed by screening for inclusion criteria. Participants deemed eligible for the study will then be sent a consent form to review and sign using through REDCap. When the Study Coordinator receives the signed consent form, participants will be mailed a pre-test/baseline assessment packet. The pre-test assessment packet will include Actigraph GT3X+ accelerometer and instructions to wear the accelerometer on the non-dominant wrist for 7 days as well as an order for blood sample collection at a Quest Diagnostics/LabCorp location that is convenient for them. Participants will complete a battery of questionnaires online using REDCap. When the Study Coordinator receives the accelerometer and notification that a blood sample has been collected, participants will be randomized into the exercise training intervention condition or attention/contact control condition using the REDCap randomization module. Following randomization, participants will be mailed their condition-specific program materials as well as instructions for downloading Zoom. All participants will receive behavioral coaching, which is founded in Social Cognitive Theory (SCT) behavior change principles. Each participant will meet one-on-one with the same behavioral coach, the PI, weekly for the first 8 weeks of the program, and biweekly for the last 8 weeks (total of 12 meetings). Meetings will be recorded for auditing and training purposes as outlined in the consent form. The research team created 12 SCT-based, condition-specific newsletters that serve as the curriculum underpinning each program. Post-test assessment of tertiary outcomes following the 16-week intervention will mirror baseline

assessments. Participants will be asked to complete an additional evaluation questionnaire to assess satisfaction with the program and usability of intervention components. All participants will be invited to complete a post-test semi-structured interview via Zoom to provide feedback on their experiences and suggestions for refining the program. All participants will be compensated \$75 for completing each assessment, and an additional \$25 will be provided for those who complete the post-test interview.

- Informed Consent: Prior to completing any assessments we will review the Informed Consent document with each participant. The member of the research team will explain each section of this document and answer any questions. Participants will be asked to sign this document using REDCap before completing assessments and being enrolled in the study. Participants will be provided with a copy of the Informed Consent document for their records.
- Blood Draw (Assessment 1&2): Participants will be asked to complete a blood draw at a Quest Diagnostics location in their local community that will take approximately 30 minutes. Biological samples will be collected and stored at Quest Diagnostics using their standardized clinical trial protocol. The samples will be disposed of immediately following analyses. They will draw 4mL of blood using a standardized protocol. This is about 1 teaspoon of blood. The biomarkers they will collect include HbA1c, cholesterol, glucose, triglycerides, and insulin.
- Questionnaires (Assessment 1&2): Participants will be asked to complete a battery of questionnaires online using REDCap at each assessment that will take 20-30 minutes. The battery of questionnaires includes a demographic and clinical characteristics questionnaire; the Patient Determined Disease Steps scale for assessing clinical disability status; the Godin Leisure Time Exercise Questionnaire; Fatigue Severity Scale; McGill Pain Questionnaire; Hospital Anxiety and Depression Scale; Multiple Sclerosis Impact Scale 29 as a quality of life measure; and the Leisure Time Physical Activity Questionnaire for People with Disabilities. Participants may skip any questions that make them feel uncomfortable.
- Physical Activity Assessment (Assessment #1&2): Participants will be asked to complete a standard 7-day accelerometry protocol using Actigraph wGT3X-bt) accelerometers (<https://actigraphcorp.com/actigraph-wgt3x-bt/>). Participants will be asked to wear the accelerometer on your non-dominant wrist during waking hours for 7 days.
- Coaching Sessions: You will be asked to join a Zoom call with your MS Behavioral Specialist coach throughout the study. The calls will consist of obtaining feedback on your progress and discussing topics relevant to your progress in the assigned program. These calls will be recorded and kept on a HIPAA compliant OneDrive folder for three years for future training and random auditing purposes then destroyed.
- Formative Evaluation (Assessment #2): Participants will be asked to complete a brief survey, online regarding your perceptions and experiences in the exercise training program that will take approximately 5-10 minutes. Participants may skip any questions that make them feel uncomfortable. We will also invite participants to complete an interview online, using Zoom that will last 20-30 minutes to provide feedback on the program they completed.
- Exercise Intervention: The exercise program includes both aerobic and strength training components to be completed over 16-weeks. The aerobic exercise prescription is progressive and individualized. Each participant starts with a goal of 10 minutes aerobic training the first 2-week period (i.e.,

accommodation period). Participants are then assigned to one of three trajectories of progression over the remaining 14-week period to reach a final goal of at least two, 30-minute aerobic workouts per week. Fifteen resistance training exercises were developed that include body weight movements and use of study-provided resistance bands or wrist weights for targeting upper body, core muscle groups, and lower body that are adaptable for manual or power wheelchair users. During the proposed program, participants will choose the resistance training exercises those that best suit their functional capabilities and goals. The resistance training prescription begins with 1 set of 10 repetitions of 5 exercises performed 2 days a week. Similar to the aerobic exercise prescription, three trajectories of progression for the resistance training will be used (i.e., sets, repetitions, and exercises) over the remaining 14 weeks to reach a final goal of at least 2 sets of 15 repetitions of 10 exercises. The participant manual includes instructions on precautions and safety for exercise that will be reviewed with all participants during the first coaching call. Coaches will check-in regularly with each participant to assess safety and report any adverse events to IRB.

- Wellness Intervention: The attention/contact wellness control condition will mirror the exercise training intervention condition, but focuses on implementing health behaviors other than physical activity (e.g., diet and emotional wellbeing) over 16 weeks. This program is an adapted version of the WellIMS program from [name] III clinical trial (NCT03490240) that [name] delivered and coached during an initial postdoctoral fellowship. The program is based on SCT principles of behavior change and integrates wellness resources from the NMSS. The research team has created 12 Newsletters split into six different topics, with each topic addressed in two newsletters. The topics include Stress Management, Emotional Regulation, Diet, Sleep, Balance and Fall Risk, and Fatigue. All coaching chats and newsletters will occur with the same frequency as in the exercise training intervention condition. Participants will be provided with a participant manual, logbook, and calendar. Participants will work with their behavioral coach on goal setting specific to wellness behaviors.

Data and Safety Monitoring

- All testing will be performed by trained personnel and all equipment will be calibrated daily before testing. If an individual indicates discomfort or the desire to discontinue testing, tests will be terminated immediately. All adverse events will be reported to the UTHealth Houston IRB and reviewed by the investigative team. Should any of these individuals and/or the IRB identify that any adverse event may be related to the study protocol, testing will be suspended and the protocol will be amended accordingly. Adverse events will be tracked using a REDCap database for assessing the primary study outcomes.

Statistics

- The planned enrolled sample size of 28 participants (i.e., 12 per group that matriculate and are randomized) is justified for pilot clinical trials when there is no prior information for sample size estimation.
- [name] (PI) will lead the data analyses given her expertise in both quantitative and qualitative data analyses. Participant characteristics will be reported using means/medians and standard deviations/interquartile ranges for continuous variables. Categorical measures will be presented as counts and percentages. The analysis will use the intent-to-treat principle where patients will be

analyzed in their randomization assignment. Descriptive statistics including frequencies and percentages will be utilized to assess the feasibility metrics for the primary and secondary outcomes (*Hypothesis 1 & Hypothesis 2*). The scientific outcomes in *Hypothesis 3* (i.e., metabolic health outcomes, MS symptoms, and exercise behavior) will be examined using 2 time by 2 group mixed factor ANOVA with estimation of Cohen's d values for effect sizes. Participant's change in scientific outcomes will be further examined and compared with the ≥ 0.5 SD will be considered meaningful change based on benchmarks established in previous research.

Ethics

- First, following screening all participants deemed eligible for the study will then be sent a consent form to review and sign using through REDCap. The PI will review the consent document to ensure participants understand study procedures and sign the document prior to enrollment. During consent process the research team will emphasize the voluntary nature of all research procedures and assess consent at each following contact as consent is an ongoing process.

Data handling and record keeping

- All paper and electronic data collected from this study will be stored in a secure location on the UTHealth Houston campus and/or a secure UTHealth Houston server for at least three (3) years past the end of this research in a locked filing cabinet behind a locked door or password protected computer in PI's campus office as appropriate. Research records will be labeled with a code and the master key linking names with codes will be maintained in a separate and secure location.
- All participants will be assigned an identification number and all data collection, as well as data analyses, will be conducted with the coded non-identifiable data; there will be no link between the ID number and the subject's name. All data will be kept in a locked file cabinet and only aggregated data will be used for presentation or publication purposes. There will not be a link between the identification number and participant for purposes of tracking participants over time. We will not maintain a link between identification number and the subject's name after completion of the study procedures, and there is no intention of linking data collected in the current project with data collected in another project. We will retain screening data for those who qualify and volunteer, and destroy the screening data for those who are excluded or do not volunteer.
- Only the members of the research team listed on the IRB application will have access to the data. Any members of the research team who are added during the study period will be submitted as an amendment to the IRB prior to having access to study data or interacting with any human subjects.

Quality control and assurance

- A data and safety monitoring plan is established to ensure the safety of all participants involved in the study and ensure validity and integrity of the collected data. The PI will be responsible for execution of this plan and data collection methods using HIPAA compliant software including REDCap. Our laboratory currently has protocols in place for participant safety and data integrity, however should the need arise a report of a serious adverse event, the appropriate forms for the UTHealth IRB will be completed with copies provided to the funder. Participants will be asked to

contact the research team via telephone or e-mail in occurrence of an adverse event or any other problem. Life-threatening adverse events will be reported within 24 hours and serious, but non-life-threatening adverse events will be reported within three days.

Publication Plan

- The research team will submit a protocol manuscript prior to initiating recruitment and primary outcomes manuscript outlining results from this study. The final results from the study will be presented at a national rehabilitation conference.
- Aggregated data will be used for presentation or publication purposes related to reporting of results and subsequent grant proposals. Data will be reported such that the identity of all participants will be protected in all publications and presentations.
- A report of the overall study findings in lay terminology will be provided to all participants following the completion of data analyses.

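### The primary safety criterion counts all adverse events alike, so it can be met after a serious exercise-related event and missed on minor events alone

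*Combined protocol and SAP*

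**What the plan says.** Study Design places safety in the primary outcome: "The primary outcome of interest is feasibility (i.e., recruitment, retention, and safety". The same section defines the measure: "Safety will be assessed in terms of incidence of participants reporting adverse events". The Objectives supply the threshold, as part of the feasibility hypothesis: "safe in terms of <10% of participants reporting adverse events". The recruitment target in that sentence is "reaching recruitment goals (n=24; 12 per group) within a one-year period", and the next sentence adds "therefore we aim to consent up to 28 participants". None of these statements names the denominator for the safety percentage.

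The Statistics section plans no test, interval or breakdown for this outcome: "Descriptive statistics including frequencies and percentages will be utilized to assess the feasibility metrics for the primary and secondary outcomes".

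Seriousness and relatedness do appear elsewhere. Under Data and Safety Monitoring, all adverse events go to the IRB and are reviewed by the investigative team. If an event is thought possibly related to the protocol, testing is to be suspended and the protocol amended. That section also says: "Adverse events will be tracked using a REDCap database for assessing the primary study outcomes". Quality control and assurance requires serious-event forms for the IRB with copies to the funder, and it sets reporting deadlines by class: "Life-threatening adverse events will be reported within 24 hours", with three days for other serious events. None of these provisions refers back to the 10% threshold.

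**The concern.** The criterion gives one participant hospitalized because of the exercise the same weight as one participant with passing soreness. What decides the result is how many people report something, whatever it is they report. The protocol needs a judgment of seriousness for its reporting deadlines and a judgment of relatedness for its suspension rule, but the primary outcome uses neither.

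At stake is the word safe in the main results. The Background presents this study as the feasibility step before a formal clinical trial, and the threshold is the only prespecified basis for a safety statement. If a serious related event occurs and the percentage is still below 10%, the plan as written supports reporting the safety hypothesis as met. Whether the event should qualify that statement would then be decided after the data are seen. The principal investigator would be closely involved in that decision, having coached the participants (Study Procedures), led the analysis (Statistics) and run the safety plan (Quality control and assurance).

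**Working it through.** **Inputs.** The threshold is strictly below 10% (Objectives). Randomized participants number 24, 12 per group (Objectives), and 2 × 12 = 24 agrees. Up to 28 are to be consented (Objectives). The documents do not derive the 10% figure, so there is no calculation of the plan's own to reproduce.

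**Step 1: which counts meet the criterion.** The percentage is x/n, where x is the number of participants with any adverse event. The rule counts people, so several events in one person count once.

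| Denominator | Largest x that meets it | Smallest x that misses it |
|---|---|---|
| Exercise arm, n = 12 | 1/12 = 8.3% | 2/12 = 16.7% |
| Both arms pooled, n = 24 | 2/24 = 8.3% | 3/24 = 12.5% |
| Consented, n = 28 | 2/28 = 7.1% | 3/28 = 10.7% |

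In every row the result depends on x alone. Making the events in the middle column serious and related, and those in the right-hand column minor, leaves the outcome unchanged.

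**Step 2: does the denominator matter?** It changes the counts but not the problem. Two affected exercise participants meet the criterion when pooled (8.3%) and miss it within their arm (16.7%), so the same data can give opposite answers until the denominator is fixed.

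**Step 3: does another section repair this?** The suspend-and-amend rule is triggered by a possibly related event of any severity. It governs conduct and says nothing about how the safety hypothesis is evaluated. The deadlines and forms govern notification. Read together, these sections allow a study to be suspended for a related event and still report its safety hypothesis as met.

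**Step 4: how easily could it happen?** Take the serious cases as given, and let each remaining participant independently report some other event with probability q. The documents give no such rate; q = 10% and q = 20% are assumptions.

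- n = 12, one serious case: the other 11 must report nothing, (1 − q)^11. This is 0.9^11 = 31% or 0.8^11 = 9%.
- n = 24, one serious case: at most one of the other 23 may report anything, (1 − q)^23 + 23q(1 − q)^22. This is 0.089 + 0.226 = 32% or 0.006 + 0.034 = 4%.
- n = 24, two serious cases: the other 22 must report nothing, (1 − q)^22. This is 0.9^22 = 10% or 0.8^22 = 0.7%.

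**Step 5: the opposite error.** With n = 24 and no serious events, the chance of meeting the criterion is P(X ≤ 2) for X binomial(24, p). It is 88% at p = 5%, 56% at 10%, 11% at 20% and 1% at 30% (again assumed rates). A program with only minor events would usually miss the criterion once such events reach about one participant in five.

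**The case against.** The strongest reply is that the protocol does not ignore seriousness or relatedness. One possibly related event of any grade leads to suspension and amendment, and serious events go to the IRB and the funder. A study with that history could hardly be presented as simply safe. This stands as a description of oversight during the trial. It does not answer the point, because the criterion would still be met on its own terms and nothing in the Statistics section commits the report to saying more.

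A second reply is that the 10% figure belongs to a hypothesis that is summarized descriptively. This also stands. A reader might infer that the plan declares the program safe, ranks programs by safety, or lets this figure decide whether a larger trial goes ahead. The documents contain no test, ranking or progression rule. Nor do they forbid a breakdown by seriousness; they simply do not plan one.

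Third, the criterion is strict because it counts any event. Step 4 shows that passing after serious cases needs few other reports, and Step 5 shows that failing on minor events may be the likelier error. That limits how often false reassurance would occur. It also confirms that the percentage is a poor guide in both directions.

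Finally, the qualifying statement proposed below rests on a relatedness judgment for which the protocol gives no criteria. That is a fair caution, but the suspension rule already depends on the same judgment.

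**Conclusion.** The concern holds as a weakness in the stated criterion. The safety hypothesis can be met with a serious related event (1 of 12 or 2 of 24, both 8.3%) and missed on minor events alone (2 of 12 = 16.7%, or 3 of 24 = 12.5%). This follows from the wording and simple proportions, and it holds for each denominator considered. Only the probabilities in Steps 4 and 5 rest on assumed rates.

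Two stronger readings are not supported. One is that two serious related events would definitely pass: that assumes pooling of both arms, which the documents do not state, and two such participants would miss the criterion within the exercise arm. The other uses the exact 95% upper limit for 1 of 12, about 38%, as evidence of the flaw. That limit is the same for a minor event, so it shows the imprecision of a small sample and says nothing about seriousness.

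This is a cheap improvement to the interpretation of a descriptive pilot outcome. It is no obstacle to running the trial.

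**What to change.** Amend the Objectives, Study Design and Statistics sections as follows.

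1. State the denominator of the safety percentage: exercise arm, all randomized, or each reported separately.
2. Commit to summarizing participants with adverse events by arm, seriousness and relatedness, alongside the overall percentage, using the judgments already made for IRB reporting and review.
3. State that meeting the 10% threshold will not by itself be reported as showing that the program is safe if any serious event judged related to the exercise program occurs.

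These changes concern how the result is reported and interpreted. The suspension and reporting rules stay as they are, as do the sample size and participant burden.

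The cost is protocol and analysis-plan wording and, if the REDCap adverse-event database does not already record these judgments, fields to hold them; the documents do not list its fields. The downside is that a safety conclusion becomes slightly harder to reach.

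### Does the acceptability hypothesis need a stated cut-off and a non-response rule, given that the PI coaches both arms and leads the analysis?

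*Combined protocol and SAP*

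**What the plan says.** In the combined protocol and SAP, Study Design ranks acceptability as the secondary outcome. Objectives measures it through post-intervention surveys and interviews and predicts that "a greater proportion of participants in the SPIN exercise training condition will report high satisfaction and positive perceptions" compared with the wellness control.

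Statistics gives the method: "Descriptive statistics including frequencies and percentages will be utilized to assess the feasibility metrics for the primary and secondary outcomes". It also states the intent-to-treat principle, with patients "analyzed in their randomization assignment".

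Under Study Procedures, the survey is online, "Participants may skip any questions that make them feel uncomfortable", and the interview is by invitation. On coaching, the same section says: "Each participant will meet one-on-one with the same behavioral coach, the PI". Statistics names the PI as lead of the quantitative and qualitative analyses. Data handling and record keeping says analyses use coded data; masking to arm is not mentioned.

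Feasibility, by contrast, has numeric targets in Objectives: 24 randomized, "retaining ≥80% of those participants through the full 16-week study period, and safe in terms of <10% of participants reporting adverse events".

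**The concern.** A comparison of proportions needs a rule for who counts as a success and a rule for who is in the denominator. Neither is written down. The survey's scale is not described, nothing says whether satisfaction and perceptions are judged separately or together, and intent-to-treat settles which arm a person belongs to but not how an absent rating is scored.

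The person best placed to make these choices knows every participant's arm, having coached them all. Background Information describes the program as "ready to be examined for feasibility before testing within a formal clinical trial", so a statement that exercise was the more acceptable program could carry weight later. If the same ratings can support either direction, the answer to the hypothesis would depend on choices made after the data are seen.

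A smaller point is that the Formative Evaluation text asks about the exercise program, which the wellness arm does not receive.

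**Working it through.** **Inputs from the plan.** 12 randomized per arm, 2 × 12 = 24. Retention of at least 80%: 0.8 × 24 = 19.2, so at least 20 retained and at most 4 lost. The plan states no rate, alpha, margin or power for acceptability, so there is no figure to reproduce.

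**Assumptions (not in the plan).** Equal true satisfaction p in both arms, from 0.6 to 0.9; non-response unrelated to satisfaction; a 5-point item for the cut-off check.

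**Denominator.** Let i of n_E exercise respondents and j of n_W wellness respondents be satisfied. Over respondents, compare i/n_E with j/n_W. Over all randomized, with missing counted as not satisfied, compare i/12 with j/12. Each probability is the sum of Bin(i; n_E, p) × Bin(j; n_W, p) over the pairs (i, j) that meet the condition. *Verdicts differ* means that exactly one rule puts exercise strictly higher, so a tie under one rule can count. *Strict reversal* means the two differences have opposite signs.

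| Respondents, exercise v wellness | Exercise higher, respondents | Exercise higher, all randomized | Verdicts differ | Strict reversal |
|---|---|---|---|---|
| 10 v 10 | 0.344-0.410 | 0.344-0.410 | 0 | 0 |
| 11 v 12 | 0.381-0.483 | 0.155-0.320 | 0.163-0.226 | 0 |
| 10 v 12 | 0.405-0.508 | 0.049-0.230 | 0.273-0.356 | 0.123-0.238 |
| 12 v 10 | 0.462-0.516 | 0.620-0.833 | 0.158-0.337 | 0.123-0.238 |
| 8 v 12 | 0.443-0.471 | 0.002-0.092 | 0.375-0.451 | 0.274-0.431 |

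Example with two missing from exercise: 9/10 − 10/12 = 90% − 83% = +7 points; 9/12 − 10/12 = 75% − 83% = −8 points.

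The effect comes entirely from unequal loss. It is zero when loss is balanced, and one missing person can produce only ties. The last row puts all the loss that the retention target allows into one arm. The all-randomized rule shifts the result against the arm with more loss, and retention is a primary outcome reported in its own right, so a reader can see the cause.

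**Cut-off.** With 12 v 12 respondents and identical multinomial distributions, nine pairs of (top, second) category probabilities were tried: (.3,.3), (.3,.4), (.3,.5), (.4,.3), (.4,.4), (.5,.3), (.5,.4), (.6,.3), (.6,.2). Comparing the top category with the top two:

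- exercise higher on one fixed cut-off: 0.359-0.419
- exercise higher on at least one: 0.547-0.595
- cut-offs differ, ties counted: 0.277-0.380
- strict reversal: 0.136-0.227

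Example: exercise 5 top, 6 second, 1 lower; wellness 7 top, 2 second, 3 lower. Top two: 11/12 − 9/12 = +17 points. Top only: 5/12 − 7/12 = −17 points.

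**What fixing the rules would gain.** With one cut-off and complete data (12 v 12), identical arms still give exercise the higher proportion in 36-42% of trials. A result of 10/12 = 83% has an exact 95% interval of 51.6-97.9%. A small numerical excess is weak evidence whether or not the rule was fixed beforehand.

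**Survey wording.** Study Procedures elsewhere refers to satisfaction with the program in general, and in the same Formative Evaluation paragraph the interview covers the program each person completed. Read together, each arm rates its own program; the exercise-only phrase is a slip.

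**The case for a change.** The strongest case for a change is that feasibility and acceptability are the purpose of this pilot. The authors set numeric criteria for the first and none for the second. A free choice between two cut-offs raises the chance that at least one favours exercise from 36-42% to 55-60% when the arms are identical, and the chooser is not masked. A few dated sentences would remove that freedom at almost no cost. The protocol manuscript promised in Publication Plan might settle the rules, but nothing says it will.

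The missing definitions and the dual role stand. So does the arithmetic, although strict reversals are less frequent than the rates that count ties. Three things weaken the case:

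- A useful cut-off depends on the survey's own scale, which these documents do not show. A request to define the term supplies no better rule.
- Two definitions would not give the hypothesis a fixed answer. How survey and interview combine, and what size of excess counts as greater, would remain open.
- Other possible additions are matters of preference. Putting respondents first sits awkwardly with the intent-to-treat sentence, which leans towards all randomized. A satisfaction benchmark for the exercise arm answers a question this comparative hypothesis does not ask, and an interval as wide as 51.6-97.9% could seldom confirm or exclude one.

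The dual role is a reason to read the descriptive claim with care. It is not evidence of bias.

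**Conclusion.** No change to the plan is needed. The gap is one of detail in a descriptive secondary outcome of a 24-person pilot, with no test, error rate or go/no-go decision attached. An analyst can fill it sensibly within the stated method: frequencies and percentages by arm can list every response category and the number responding, which exposes any dependence on cut-off or denominator.

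The sensitivity is real but bounded. Strict reversal occurs in about 14-23% of trials for a one-category change of cut-off, and in about 12-24% for the denominator when two people are missing from one arm only. It rises to 27-43% in the extreme case of four lost from one arm and none from the other, and is zero with balanced loss. These figures rest on equal true satisfaction of 60-90% (for the cut-off, the identical category distributions listed), non-response unrelated to satisfaction, and an assumed 5-point item. The main limit on the acceptability conclusion is 12 people per arm, which a pre-stated rule would not alter. The survey wording is a clerical slip.
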